4. TRIAL SCHEDULE

There will be three appointments including the baseline appointment and two follow-up appointments (6 weeks and 12 weeks) after therapy. The details of each visit will be mentioned in 6.3. Study Visits and Procedures.

5. STUDY DESIGN

5.1 Summary of Study Design

This is randomized double blinded clinical control study designed to assess improved clinical and microbiological outcomes with the use of laser antimicrobial photodynamic therapy (aPDT) as an adjunct to the gold standard of mechanical debridement in the treatment of peri-implant diseases. Seventy-four patients will be recruited. Clinical measurements including bleeding on probing, pocket depth, plaque, and clinical attachment will be measured at baseline, 6 weeks, and 12 weeks after therapy. The 2017 World Shop classification will be used to diagnosis implants as peri-implant mucositis or peri-implantitis (as stated above in section 3.3). Only diseased implants will be included and only one implant per patient will be studied. The hypothesis is that inflamed implant sites treated with mechanical debridement and adjunctive aPDT will have greater reduction in bleeding and pocket depth reduction than those sites treated with mechanical debridement alone. The potential for greater healing and greater antibacterial activity on the implant surface will benefit patients who have peri-implant diseases. The results can be applied in the managing and in the armamentarium for treatment of both peri-implantitis and peri-implant mucositis.

6. METHODS AND ASSESSMENTS

6.1 Randomization and Blinding

Therapy group allocation (test or control) will be performed by the investigators before treatment is rendered based on computer-generated randomized (R Statistical Software). Two blinded examiners will be used to take clinical measurements (presence/absence of Plaque, BOP, PPD, CAL) at baseline, and then six and twelve weeks after treatment. Patients in the control group will be blinded by performing mechanical debridement plus a “sham” aPDT (saline with non-light emitting laser).

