Mechanical debridement with curettes of implant surfaces have been shown to reduce and reverse peri-implant inflammation. Antimicrobial photodynamic therapy, used with a diode laser, works through an interaction between the photosensitizer (methylene blue or toluidine blue), red light (625–740 nm), and oxygen. The methylene blue dye is taken up by the bacteria and the visible red light excites the dye. The excited dye transfers energy to tissue oxygen forming a singlet oxygen molecule. Singlet oxygen is highly reactive and will affect the bacterial cell by damaging the cell membrane and cell wall. The bactericidal effect is through DNA damage and more importantly damage to the cytoplasmic membrane (Takasaki *et al.* 2009). The photosensitizer, such as methylene blue, undergoes a strong cationic charge, which can bind to the outermost membrane of gram-negative bacteria and can penetrate bacterial cells. This creates selectivity of the dye to affect bacterial cells rather than human tissue cells (Takasaki *et al.* 2009). Also, the singlet oxygen molecule has a short lifetime and limited migration, so the reaction and cellular damage is contained within a limited space (Takasaki *et al.* 2009).

c. Rationale for Study Population

The study will recruit subjects who have an implant diagnosed with either peri-mucositis or peri-implantitis based on the 2017 World Workshop periodontal classification (Renvert *et al.* 2018). The gold standard to treatment inflammation around implants is mechanical debridement. All patients recruited are in need of traditional mechanical debridement.

d. Rationale for Study Design

It is a randomized double blinded clinical control study. The randomized controlled trial (RCT) is usually considered the gold standard for a clinical trial and it is able to provide the highest level of evidence within all the study designs. Two treatments (test and control) are randomly assigned to a single implant for each patient. Both the examiners and patient will be blinded to which treatment was completed. The investigator completing the treatment will not be blinded. This design removes examiner and patient bias and placebo effects.

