6.3 Study Visits and Procedures

a. Screening Visits and Procedures

Study protocol and consent forms will be approved by the Institutional Review Board at the University of Texas Health Science Center at Houston. The trial will be registered with ClinicalTrials.gov. The clinicians treating patients at UTSD will be told the information of this clinical trial. The potential subjects will be identified in the clinic of Department of Periodontics, Prosthodontics, or UTDentists for initial screening. The principal investigator will confirm the eligibility of these patients.

All patients will sign the consent forms and will be informed of the details of study procedures as well as potential complications. After informed consent is obtained, the non-surgical implant therapy will be scheduled as the first visit.

Patient's Demographic Data Collection

Upon enrollment into the study and patient's consent form signed, patient's demographic data from patient's electronic health record (EHR) in the UT School of Dentistry will be collected. This information will include, but not limited to, patient's de-identifiable chart number, age, gender, race, medical history, dental conditions, and all pertinent dental implant related data. Radiographic information regarding the implant(s) included in the study will also be collected prior to treatment.

b. Study Visits and Procedures

Patients will be randomly divided into 2 treatment groups. (A) Test group: patients will undergo traditional non-surgical mechanical debridement with adjunctive use of aPDT at implant(s). (B) Control group: patients will undergo traditional non-surgical mechanical debridement alone with “sham” aPDT with saline and non-light emitting laser at implant(s). Clinical measurements and PISF will be collected at the baseline appointment, and at follow up 12 weeks after treatment. For PISF collection, the volume of fluid collected will be measured using Periotron then stored in -80° C freezer. Plaque samples will be taken at baseline and at the 12-week appointment. Full mouth prophylaxis or periodontal maintenance will be completed with ultrasonics, hand instruments, and prophylaxis paste. Oral hygiene instructions will be

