reviewed with all patients including techniques to clean around implants. Mechanical debridement of implant surfaces will be completed with titanium scalers and ultrasonics removing supragingival and subgingival plaque. Antimicrobial photodynamic therapy will be done at implant sites by applying a photosensitizing dye methylene blue (0.1 mg/ml) with a disposable syringe from the bottom of pocket in a coronal direction. The methylene blue dye will be diluted from 1.0% to 0.1% before use. The dye will be applied topically confined to the epithelialized space surrounding the implant fixture and will not be internalized. After 5 minutes in situ, the surrounding gingival tissues will be irradiated at six sites around the implant using a diode laser with a wavelength of 660nm, providing an energy density of 10 J/site, 100mW power, time equal to 100 seconds. After irradiation, the site will be thoroughly rinsed with saline. Only pockets \geq 4mm will be treated with the diode laser as this is the threshold pocket for diagnosing peri-implant inflammation per the 2017 World Work Workshop (Heitz-Mayfield & Salvi, 2018).

Clinical Measurements

Implant sites will be evaluated at baseline, six weeks, and twelve weeks after treatment (2 follow-up visits in total). Improvement in sites resulting from a reduction in inflammation will be analyzed based on pocket depth, clinical attachment loss, bleeding on probing, and the presence of plaque. For clinical measurements, six sites around the implant will be measured: mesial buccal, mid buccal, distal buccal, mesial lingual, mid lingual, and distal lingual. Bleeding on probing will be evaluated by gently sweeping the periodontal probe just within the gingival sulcus of the implant and the presence or absence of bleeding will be recorded. The presence or absence of plaque will then be evaluated at six sites around the implant surface. Plaque sampling will be performed prior to the remaining clinical measurements at the baseline/treatment appointment and 12 weeks after treatment utilizing a titanium curette within the gingival sulcus of the inflamed site. Periodontal pocket depth is measured from the free gingival margin to the base of the pocket, with a UNC periodontal probe with 1mm measurement units. Clinical attachment loss is measured by subtracting the pocket depth from distance of the free gingival margin to the implant platform.

Microbiologic collection and analysis

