8.3 Blinding

The investigator performing the treatment cannot be blinded because they will know if the dye has been applied and if the laser has been activated. Patient will be blinded because the control group will use a sham procedure including the use of saline and non-light emitting laser. The examiners will be blinded. The patients will be informed of benefits of all the procedures and realize that a minimum they are receiving the gold standard of peri-implant treatment, mechanical debridement.

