11.2 Statistical and Analytical Plans

a. General Consideration

We will present means and standard deviations for completeness of the report. The statistical significance level to test the primary endpoint was set at $p<0.05$.

b. Safety Analyses

Safety will be evaluated by tabulations of adverse events and will be presented with descriptive statistics at baseline and follow-up visits each month.

Adverse events will be classified as severe complications and summarized for baseline and follow-up visits.

All information pertaining to adverse events noted during the study will be listed by subject, detailing verbatim given by the investigator, preferred term, date of onset, date of resolution, severity, and relationship to procedure. The onset of adverse events will also be shown relative (in number of days) to the day of performing the surgery.

c. Statistical Analysis Plan

We will analyze these data sets using generalized linear mixed effects models with the appropriate error structure (e.g., binomial, poisson) and specifying treatment (control mechanical debridement vs mechanical debridement + aPDT) as a fixed factor and repeated measures of individuals over 0, 6, and 12 weeks as a random factor. Demographic data collected from patients will be included in analysis and will be adjusted for any confounders. All quantitative analyses will be performed in R Statistical Software (R Core Team 2017).

For microbiologic analysis, microbial DNA will be purified using the QIAmp DNA Mini Kit (Qiagen, Hilden, Germany) or Qiagen DNA MiniAmp kit (Qiagen, Valencia, CA, USA), according to the manufacturer's protocol. 16S rRNA gene V4 amplification and sequencing will be completed. 16S rRNA gene data analysis will also be completed for the plaque samples.

For immunologic analysis, the PerioPaper strips will be analyzed using multiplexed fluorescent bead-based immunoassay. Assessments will be made in triplicate, and for the statistical analysis, median of the replicates will be used.

12. Ethical Consideration

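### The randomisation list is not stated to be concealed, and nothing withholds the arm from the unblinded operator until the debridement common to both arms is finished

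*Combined protocol and SAP*

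**What the plan says.** On who allocates and when, section 6.1 says: "Therapy group allocation (test or control) will be performed by the investigators before treatment is rendered". It adds that the sequence is computer-generated in R. It does not say who holds the list, whether upcoming assignments are hidden, or at what moment the operator learns the result.

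On blinding, section 1.2 d says "Both the examiners and patient will be blinded to which treatment was completed" and then "The investigator completing the treatment will not be blinded". Section 8.3 gives the reason: "The investigator performing the treatment cannot be blinded because they will know if the dye has been applied", and likewise whether the laser was switched on.

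On the procedure common to both arms, section 6.3 b gives mechanical debridement to the test group with aPDT and to the control group with a sham (saline and a laser that emits no light). Its delivery is described in one sentence: "Mechanical debridement of implant surfaces will be completed with titanium scalers and ultrasonics removing supragingival and subgingival plaque".

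On the analysis, section 11.2 c fits mixed models "specifying treatment (control mechanical debridement vs mechanical debridement + aPDT) as a fixed factor".

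**The concern.** Debridement is the working treatment in both arms. Section 1.1 calls mechanical plaque removal the gold standard, and section 1.2 b says it reduces and reverses peri-implant inflammation. It therefore acts directly on the two primary outcomes, bleeding on probing and probing depth.

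If the operator knows the arm while debriding, thoroughness can differ by arm without anyone intending it. The operator might work harder where aPDT is to follow, or compensate patients who will get only the sham. Either way, the difference between arms would no longer isolate aPDT. Examiner and patient blinding protect measurement and patient response, not the delivery of the shared procedure. Nor can the analysis recover the lost balance, since the plan records nothing about how much debridement each patient received.

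A related exposure arises before treatment. Section 3.3 requires at least one diseased implant and section 5.1 studies only one per patient, but no rule says which. Without a concealed list, enrolment or choice of implant could be influenced by the next assignment.

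**Working it through.** The plan states no figure for this risk, so the main check sets the sections side by side.

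1. **Timing.** Allocation precedes treatment (6.1). Treatment includes debridement in both arms (6.3 b). So the arm exists before debridement starts.
2. **Who may know it.** The operator is an investigator and is unblinded (1.2 d, 8.3), and investigators do the allocating (6.1). No section separates the two roles, delays disclosure, or gives debridement to a blinded operator.
3. **Whether it has to be known then.** The reason in 8.3 is limited to the dye and the laser. In 6.3 b the text describes prophylaxis, hygiene instruction and debridement first, and dye and laser afterwards. Nothing before the dye step requires knowledge of the arm.
4. **Room for discretion.** Section 6.3 b names the instruments and the plaque to be removed. It gives no duration, completion criterion, operator calibration or fidelity record.
5. **Where a difference would go.** The treatment term in 11.2 c compares whole packages. If the arms differ by aPDT effect A plus debridement difference B, the term estimates A + B. B may have either sign.

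**Illustration only.** Inputs: n = 32 per arm and alpha 0.05 (section 3.1); two-sided testing (assumed, as sidedness is not stated); a two-sample t-test on a continuous outcome (assumed, and not the planned model); B in SD units (assumed).

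Noncentrality = (A + B) × √(n/2) = (A + B) × √16 = 4(A + B), with 2 × 32 − 2 = 62 degrees of freedom.

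| A (SD) | B (SD) | Noncentrality | Two-sided rejection rate |
|---|---|---|---|
| 0 | 0 | 0 | 5.0% |
| 0 | 0.1 | 0.4 | 6.8% |
| 0 | 0.2 | 0.8 | 12.4% |
| 0 | 0.3 | 1.2 | 21.9% |
| 0.8 | 0 | 3.2 | 88.3% |
| 0.8 | −0.2 | 2.4 | 65.6% |

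The first four rows show false positives. Their rates are the same if B has the opposite sign, but most rejections would then favour control. The last two rows show the loss of power if operators compensate controls by 0.2 SD. The value A = 0.8 is an assumed reading of the large effect in section 3.1, which gives no number.

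**The case against.** The strongest reply is that the documents are silent rather than wrong. Section 6.1 does not say when in the visit allocation happens, who learns the result, or that the person allocating is the person treating. Section 8.3 is compatible with an operator who learns the arm only on picking up the dye or saline. A reader might infer that the arm is disclosed before the session starts and that all debridement is done with the arm known. The text does not say that, and the order of debridement before aPDT is itself taken from the order of the description. This part of the objection stands: the supportable claim is that the operator may know the arm, because nothing prevents it.

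A reader might also infer that investigators can see upcoming assignments. That is not stated either. Section 6.3 describes eligibility confirmation and consent before it comes to random division. That order does not amount to concealment, but it is not evidence of foreknowledge.

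The plan also has partial safeguards: operator unblinding is disclosed and explained, the debridement instruments and target are the same in both arms, and patients and examiners are blinded. These narrow the routes for bias. They do not cover how thoroughly an operator who may know the arm carries out a loosely specified procedure.

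Finally, the percentages rest on assumed shifts and a t-test, whereas section 11.2 c plans generalized linear mixed models with repeated measures. That also stands. They are not this trial's error rate.

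**Conclusion.** The point holds as a gap that leaves an avoidable risk of performance bias. It is neither a contradiction in the plan nor evidence that operators would treat the arms differently. The protocol does not state how the list is concealed or when the operator learns the arm, and its own reason for unblinding does not extend to the debridement.

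The size of any bias cannot be estimated from the documents, and its direction is unknown. If effort differed by an assumed 0.1 to 0.3 SD, a simple t-test with no aPDT effect would reject about 7% to 22% of the time. If controls were favoured by an assumed 0.2 SD, power at an assumed effect of 0.8 SD would fall from about 88% to 66%. The conclusion does not depend on these figures. It rests on the absence of any stated safeguard and on how cheaply one can be added. The change should be made before treatment begins, because analysis cannot supply it afterwards.

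**What to change.** In section 6.1, state that:

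- a team member who neither enrols nor treats generates and holds the R list;
- each assignment is sequentially numbered and concealed (opaque sealed envelope or locked electronic file);
- it is opened only after eligibility, choice of study implant, baseline examination, sampling, prophylaxis and debridement are complete, immediately before the aPDT or sham step.

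Align sections 1.2 d and 8.3, so that the operator is described as unblinded from that step onward.

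Reconcile the timing of oral hygiene instruction. Section 6.3 b mentions it before debridement, while section 8.2 places it after treatment. For the comparison, it should either be given before the assignment is opened or be delivered in the same scripted way in both arms.

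Recording debridement time and completion for every patient would be a useful addition, since it would let the balance between arms be shown.

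The cost is a few sentences across these sections, a set of envelopes or a locked file, and one person outside enrolment and treatment. The practical downside is that both dye and sham materials must be ready at the chair for every patient. Sample size, visits and the analysis model do not change.

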6.2 Contraception and Pregnancy Testing

Pregnancy status of subjects who are women with childbearing potential will be orally confirmed at the screening. The pregnant subjects will be excluded from the study.

6.3 Study Visits and Procedures

a. Screening Visits and Procedures

Study protocol and consent forms will be approved by the Institutional Review Board at the University of Texas Health Science Center at Houston. The trial will be registered with ClinicalTrials.gov. The clinicians treating patients at UTSD will be told the information of this clinical trial. The potential subjects will be identified in the clinic of Department of Periodontics, Prosthodontics, or UTDentists for initial screening. The principal investigator will confirm the eligibility of these patients.

All patients will sign the consent forms and will be informed of the details of study procedures as well as potential complications. After informed consent is obtained, the non-surgical implant therapy will be scheduled as the first visit.

Patient's Demographic Data Collection

Upon enrollment into the study and patient's consent form signed, patient's demographic data from patient's electronic health record (EHR) in the UT School of Dentistry will be collected. This information will include, but not limited to, patient's de-identifiable chart number, age, gender, race, medical history, dental conditions, and all pertinent dental implant related data. Radiographic information regarding the implant(s) included in the study will also be collected prior to treatment.

b. Study Visits and Procedures

Patients will be randomly divided into 2 treatment groups. (A) Test group: patients will undergo traditional non-surgical mechanical debridement with adjunctive use of aPDT at implant(s). (B) Control group: patients will undergo traditional non-surgical mechanical debridement alone with “sham” aPDT with saline and non-light emitting laser at implant(s). Clinical measurements and PISF will be collected at the baseline appointment, and at follow up 12 weeks after treatment. For PISF collection, the volume of fluid collected will be measured using Periotron then stored in -80° C freezer. Plaque samples will be taken at baseline and at the 12-week appointment. Full mouth prophylaxis or periodontal maintenance will be completed with ultrasonics, hand instruments, and prophylaxis paste. Oral hygiene instructions will be

reviewed with all patients including techniques to clean around implants. Mechanical debridement of implant surfaces will be completed with titanium scalers and ultrasonics removing supragingival and subgingival plaque. Antimicrobial photodynamic therapy will be done at implant sites by applying a photosensitizing dye methylene blue (0.1 mg/ml) with a disposable syringe from the bottom of pocket in a coronal direction. The methylene blue dye will be diluted from 1.0% to 0.1% before use. The dye will be applied topically confined to the epithelialized space surrounding the implant fixture and will not be internalized. After 5 minutes in situ, the surrounding gingival tissues will be irradiated at six sites around the implant using a diode laser with a wavelength of 660nm, providing an energy density of 10 J/site, 100mW power, time equal to 100 seconds. After irradiation, the site will be thoroughly rinsed with saline. Only pockets \geq 4mm will be treated with the diode laser as this is the threshold pocket for diagnosing peri-implant inflammation per the 2017 World Work Workshop (Heitz-Mayfield & Salvi, 2018).

Clinical Measurements

Implant sites will be evaluated at baseline, six weeks, and twelve weeks after treatment (2 follow-up visits in total). Improvement in sites resulting from a reduction in inflammation will be analyzed based on pocket depth, clinical attachment loss, bleeding on probing, and the presence of plaque. For clinical measurements, six sites around the implant will be measured: mesial buccal, mid buccal, distal buccal, mesial lingual, mid lingual, and distal lingual. Bleeding on probing will be evaluated by gently sweeping the periodontal probe just within the gingival sulcus of the implant and the presence or absence of bleeding will be recorded. The presence or absence of plaque will then be evaluated at six sites around the implant surface. Plaque sampling will be performed prior to the remaining clinical measurements at the baseline/treatment appointment and 12 weeks after treatment utilizing a titanium curette within the gingival sulcus of the inflamed site. Periodontal pocket depth is measured from the free gingival margin to the base of the pocket, with a UNC periodontal probe with 1mm measurement units. Clinical attachment loss is measured by subtracting the pocket depth from distance of the free gingival margin to the implant platform.

Microbiologic collection and analysis

Plaque samples will be taken from the deepest probing site of each implant before and 12 weeks after PDT. If more than one sites presented similar probing values, the most anterior site would be chosen for ease of obtaining an appropriate sample. The sample sites will first be isolated by cotton rolls and supragingival and marginal plaque will be removed before subgingival biofilm samples collected using sterile titanium implant scalers (Hu-Friedy). The collected samples will be immediately placed in separate sterile Eppendorf tubes containing 0.15 ml TE (10 mM Tris-HCl, 1 mM EDTA, pH 7.6). Samples will be stored at -80°C until further analysis. DNA will be purified using the QIAamp DNA Mini Kit (Qiagen, Hilden, Germany) or Qiagen DNA MiniAmp kit (Qiagen, Valencia, CA, USA), according to the manufacturer's protocol. 16S rRNA gene V4 amplification and sequencing will be completed. 16S rRNA gene data analysis will also be completed for the plaque samples.

PISF collection and analysis

PISF will be collected from the sulcus around the target dental implant using paper strips (PerioPaper, Oraflow). In patients with multiple implants, preference will be given to the implant included in the study. With proper isolation using cotton rolls in the buccal and lingual aspects of the study site, the area will be dried for 5 seconds with compressed air. The paper strip will be gently introduced into the

mucosal crevice around the dental implant for 30 seconds per site in four sites (mesial, distal, facial/buccal, lingual/palatal). The strips will then be removed from the crevice, and the volume of fluid collected in each strip measured using a micromoisture metering device (Peritron, Oraflow). After confirming the adequateness of the volume, the paper strips from each implant will be transferred into labeled tubes and stored at -80° C for later use. For analysis, the paper strips will be analyzed using multiplexed fluorescent bead-based immunoassay. Assessments will be made in triplicate, and for the statistical analysis, median of the replicates will be used.

c. Final Study Visit

The twelve weeks follow up will be the subjects last visit for this clinical trial. The patient will have clinical measurements taken as previously mentioned as well as possible radiographic measurements. If the patient has been diagnosed with peri-implant mucositis, recommendations will be made for continued maintenance of the diseased implant(s) and follow every 3 months. If the patient has been diagnosed with peri-implantitis, recommendations will be made for the possible need for surgical treatment.

d. Post Study Follow up and Procedures

[figure not shown]
The subjects will continue having routine maintenance appointments and/or treatments to follow up the outcomes related to the surgery and periodontal health in the periodontics clinic of UTSD. If the patients have symptoms or complications, the necessary treatments, will be performed.

e. Discontinuation Visit and Procedures

Subjects are free to withdraw from participation in the study at any time upon request. A subject may be discontinued from participation in the study for any of the following reasons:

1. Withdrawal of consent
2. Subject noncompliance with the protocol, as determined by the investigator
3. Any event or condition that would make continued participation in the study not in the best interest of the subject, as determined by the investigator
4. Pregnancy
5. Development of any medical condition that might affect the treatment and clinical outcomes, as determined by the investigator.
6. Initiation of any treatment or exposure that might affect the outcomes of implant therapy, as determined by the investigator.
7. Investigator discretion

Any subject with a serious adverse event, such as life-threatening diseases, hospitalization, that is ongoing at the time of discontinuation will be followed until the event returns to baseline, resolves, or stabilizes. If the serious adverse event does not meet these outcomes within 30 days after discontinuation or after study completion, the subject will be referred to an appropriate practitioner for continued care. If the study is discontinued, subjects will be referred back to the qualified clinicians for necessary dental care.

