7. TRIAL MATERIALS

7.1 Trial Products

Diode laser (660nm) will be used in conjunction with methylene blue photosensitizing dye. Antimicrobial photodynamic therapy uses low level laser light and aims to destroy pathogens around the implant and can also act as a photobiomodulator reducing inflammation and stimulating cellular proliferation (Mizutani et al. 2016). Antimicrobial photodynamic therapy works through an interaction between the photosensitizer (methylene blue or toluidine blue), red light (625–740 nm), and oxygen. The methylene

blue dye is taken up by the bacteria and the visible red light excites the dye. Excited dye transfers energy to tissue oxygen forming a singlet oxygen molecule. Singlet oxygen is highly reactive and will affect the bacterial cell by damaging the cell membrane and cell wall. The bactericidal effect is through DNA damage and more importantly damage to the cytoplasmic membrane (Takasaki et al. 2009). To activate the photosensitizer, the laser light can be delivered via a fiber placed into the pocket or transmitted through the mucosa. Saffarpur et al. (2018) through an in vitro study evaluated implants treated with aPDT and found no change in the implant surface. Neither the dye nor the low-level energy laser changed the implant surface characteristics. aPDT applied to rough titanium or zirconia surfaces have maintained the surface integrity of the treated implants. (Azizi et al. 2018, Giannelli et al. 2017). The photosensitizer, such as methylene blue, undergoes a strong cationic charge, which can bind to the outermost membrane of gram-negative bacteria and can penetrate bacterial cells. This creates selectivity of the dye to affect bacterial cells rather than human tissue cells (Takasaki et al. 2009). Also, the singlet oxygen molecule has a short lifetime and limited migration, so the reaction and cellular damage is contained within a limited space (Takasaki et al. 2009).

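### The methylene blue strength is given as both 0.1 mg/ml and 0.1%, which differ tenfold, so the dose of the test agent is not uniquely defined

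*Combined protocol and SAP*

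**What the plan says.** The dye is described in section 6.3 b (Study Visits and Procedures). The test procedure delivers "photosensitizing dye methylene blue (0.1 mg/ml) with a disposable syringe", filling the pocket from its base upwards. The next sentence is the preparation instruction: "The methylene blue dye will be diluted from 1.0% to 0.1% before use".

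The remaining treatment settings follow in the same paragraph. The dye is left in place ("After 5 minutes in situ") and the tissue is then irradiated at 660 nm, "providing an energy density of 10 J/site, 100mW power, time equal to 100 seconds".

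Section 7.1 (Trial Products), where a reader would look for the strength of the product, says only "Diode laser (660nm) will be used in conjunction with methylene blue photosensitizing dye". The other places that mention the dye are the rationale for materials (1.2 b), the safety risks (2.4 b) and blinding (8.3). None of them gives a concentration.

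**The concern.** A concentration in mg/ml and a concentration in percent can describe the same solution, but these two do not. The first is attached to the dye as it goes into the pocket, the second to the dye as made ready for use. They should therefore be the same number in different units, and they are a factor of ten apart.

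Section 1.2 b describes the therapy as an interaction of photosensitiser, red light and oxygen. The trial sets the first two, so dye strength is one of the main parameters defining the test arm. Three things are at stake:

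- **Delivery.** Someone working from the dilution sentence makes a dye ten times stronger than someone working from the mg/ml figure. Each could claim to have followed the protocol, and a preparation deviation could not be judged against the text.
- **Interpretation.** Section 11.2 c models treatment as a single two-level factor with no term for dye strength. If both strengths were used, the estimated effect would average over two versions of the treatment and the planned analysis would not show it.
- **Reproducibility and risk description.** A later reader could not tell which strength was tested. Section 2.4 b names reversible gingival staining as a risk of the dye without saying at what strength.

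**Working it through.** **Inputs, all from section 6.3 b**

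- Concentration as applied: 0.1 mg/ml
- Stock: 1.0%
- Strength after dilution: 0.1%

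**Conversion.** Percent w/v is grams per 100 ml. Since 1 g is 1000 mg, mg/ml = % × 1000 / 100 = % × 10.

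**Attempt to reproduce the stated 0.1 mg/ml from the stated dilution**

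- Stock: 1.0 × 10 = 10 mg/ml
- After dilution: 0.1 × 10 = 1 mg/ml
- Ratio to the stated concentration: 1 / 0.1 = 10

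The figure is not reproduced; the described preparation is ten times stronger.

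**The same check in the other direction**

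- 0.1 mg/ml as a percentage: 0.1 / 10 = 0.01% w/v
- Dilution described: 10 / 1 = 10-fold
- Dilution needed to reach 0.1 mg/ml: 10 / 0.1 = 100-fold

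**Does another meaning of percent close the gap?** On a weight-per-weight reading, 0.1% is 0.001 × density × 1000 mg/ml. The documents give no density. Over an assumed range of 0.99 to 1.05 g/ml the result is 0.99 to 1.05 mg/ml, still about ten times 0.1 mg/ml.

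**The two possible corrections**

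| If the intended strength is | First sentence | Second sentence | Dilution of 1.0% stock |
|---|---|---|---|
| 0.1 mg/ml | stands | must read 0.01% | 100-fold |
| 0.1% | must read 1 mg/ml | stands | 10-fold |

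**The light settings, checked for comparison.** 100 mW is 0.1 W, and 0.1 W × 100 s = 10 J, which agrees with the stated 10 J per site. The problem is confined to the dye.

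**The case against.** The best counter-argument is that only one of the two sentences is an instruction. The dilution sentence gives a starting and a finishing strength, hence a single tenfold dilution, and staff who follow it will all make the same solution. The mg/ml figure is a parenthesis and may simply be a unit slip. If the clinic prepared one strength throughout, every test subject received the same treatment, the randomised comparison is intact, and only the description needs correcting. Everything else about the intervention (delivery, incubation time, wavelength, power, duration, pocket threshold, rinse) is given. The documents contain no concentration-response information, and the staining risk is described only qualitatively, so no harm from a tenfold difference has been shown.

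Much of this stands. The text does not show that operators varied, and an effect on efficacy or staining cannot be inferred from the documents. Allocation, blinding, endpoints, sample size and the analysis model are untouched.

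It does not remove the discrepancy. A unit slip is the likely cause, but the documents do not show which sentence contains it. The parenthesis is attached to the dye as applied, so preparing to that figure is also a fair reading of the protocol. Even with fully consistent preparation, the protocol would misstate the dose in one of two adjacent sentences.

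**Conclusion.** The concern holds and should be corrected. The two stated strengths of the test agent, 0.1 mg/ml and 0.1% (1 mg/ml), differ by a factor of 10, exactly so on a w/v reading and approximately so on a w/w reading with density near 1 g/ml. The only assumptions are the usual meaning of percent and that both sentences describe the final solution; no further dilution step is described.

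The ambiguity applies to the written treatment of the whole test arm: the 32 subjects planned for analysis in section 3.1, or 74 / 2 = 37 if all 74 recruits are randomised equally. It does not establish that subjects received different strengths, nor that the difference matters clinically. It is a must-fix because it concerns the dose of the agent under test, both statements cannot be followed, and nothing elsewhere in the documents resolves them.

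**What to change.** Replace the two statements in section 6.3 b with one concentration, written in both mg/ml and % w/v, together with the stock strength and the dilution factor. Repeat that figure in section 7.1 and in the treatment instructions, and add it to the data collection form (Appendix 1, whose content is not shown) if it is not already there. The sponsor must say which value is intended; this review does not choose between them.

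If subjects have already been treated, establish from whatever preparation records exist the strength each one received, and record it per subject. If more than one strength turns out to have been used, report this with the results.

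The cost is a short protocol correction, the IRB approval that section 12.2 requires for any amendment, and a check of records where treatment has started. Sample size, visit schedule and analysis model do not change.
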